### PLANNED ENROLLMENT REPORT

Racial Categories	DOMESTIC PLANNED ENROLLMENT REPORT (TREATMENT)				Total	
	Ethnic Categories					
	Female	Male	Female	Male		
American Indian/ Alaska Native	0	0	0	0	0	
Asian	1	1	0	0	2	
Native Hawaiian or Other Pacific Islander	0	0	0	0	0	
Black or African American	3	3	0	0	0	
White	12	12	1	1	26	
More Than One Race	1	1	0	0	2	
Total	17	17	1	1	36	

PHS 398 / PHS 2590 (Rev. 03/20 Approved Through 2/28/2023)

OMB No. 0925-0001/0002

### 9.3 Analysis of Secondary Endpoints

Adverse events and DLTs will be summarized by frequency and magnitude. The rate of feasibility of administering entinostat concomitantly with atezolizumab, carboplatin, and etoposide as determined by the proportion of participants who receive 3 or more cycles of the combination, will be calculated with a 90% confidence interval. The Kaplan Meier estimator will be used to estimate survival curves for all time to event endpoints including progression free survival (PFS) and overall survival (OS). The 9 month PFS rate will be estimated with a 90% confidence interval. Anti-tumor endpoints, including measures of tumor response and symptom relief, will be summarized using descriptive statistics. Tumor response will be measured using RESIST 1.1 criteria and reported as overall response rate (ORR) with a 95% confidence interval. Entinostat exposure will be determined for each patient using mixed effects pharmacokinetic modeling. Atezolizumab clearance, including a time-varying rate of change, will be determined for each patient using mixed effects pharmacokinetic modeling. Exposure-response assessments will be assess associations between entinostat exposure with the clinically significant toxicity, PFS and OS. Clearance-response will be assessed between baseline or time-varying atezolizumab clearance with the presence of cachexia, PFS and OS. Biomarker evaluations from exploratory objectives will be summarized using descriptive statistics.

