## **1. OBJECTIVES**

### **1.1 Primary Objectives**

- 1.1.1 To determine the maximum tolerated dose (MTD) of entinostat in combination with carboplatin, etoposide, and atezolizumab.
- 1.1.2 To determine safety and tolerability of adding entinostat to carboplatin / etoposide / atezolizumab for extensive-stage small cell lung cancer (ES-SCLC).
- 1.1.3 To determine the feasibility of administering entinostat concomitantly with atezolizumab, carboplatin, and etoposide as determined by the proportion of patients who receive 3 or more cycles of the combination.

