### 2.4.2.2 Clinical Data

In a phase II trial of 76 patients with non-small cell lung cancer (NSCLC) previously treated with checkpoint inhibitors, the combination of entinostat 5 mg orally given weekly with pembrolizumab 200 mg IV every 3 weeks resulted in an objective response rate of 10% (Hellmann *et al.*, 2018b). Responses were seen in patients regardless of prior response to checkpoint inhibitors or PD-L1 status. The combination of entinostat and pembrolizumab was tolerable with only 14% of patients discontinuing treatment due to a treatment-related adverse event; 17% required a dose reduction of entinostat; and thrombocytopenia and anemia, grade 1-2 were reported at 15% and 12%, respectively, and grade 3-4 were reported at 1% and 7%, respectively.

The combination of entinostat with both immunotherapy and chemotherapy has not been studied. Due to potential overlapping toxicity, particularly hematologic toxicity, with entinostat and carboplatin and etoposide chemotherapy, this study will evaluate entinostat at 3 mg weekly, which is below the recommended phase two dose of 5 mg weekly. There will also be a phased-in start of entinostat after the completion of 4 cycles of carboplatin and etoposide, if necessary, due to toxicity.

In summary, SCLC is a recalcitrant cancer with poor prognosis. The addition of atezolizumab to carboplatin/etoposide chemotherapy has resulted in an improvement in overall survival, but further improvements are needed as the overall survival in this patient population is approximately 1 year. HDAC inhibition may be particularly useful in this disease due to immunomodulatory effects as well as direct antitumor effects, particularly in tumors with *CREBBP* or *EP300* loss, which may be as prevalent as 25-30% of patients. Entinostat has shown immunomodulatory effects by reducing MDSCs and Tregs and has demonstrated safety (low hematologic toxicity) and efficacy in combination with pembrolizumab in patients with NSCLC, making it an ideal HDACi to combine with chemotherapy. Based on this, we propose a phase I

trial of carboplatin, etoposide, atezolizumab, and entinostat for patients with previously untreated extensive-stage SCLC.

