## 6. TREATMENT PLAN

### 6.1 Agent Administration

Treatment will be administered on an outpatient basis (inpatient is allowed if clinically indicated). Reported adverse events and potential risks are described in Section 10. Appropriate dose modifications are described in Section 7. No investigational or commercial agents or therapies other than those described below may be administered with the intent to treat the patient's malignancy.

Patients will receive up to 4 cycles of induction treatment followed by maintenance treatment for a total of 1 year of combined treatment (or 17 cycles). Patients who are unable to tolerate carboplatin and etoposide may discontinue induction and receive maintenance treatment for the remaining duration of treatment. Order of administration during induction should be according to institutional standard. Entinostat should be taken prior to administration of other agents.

On day 1, when patient receives additional therapy, entinostat will be administered prior to other chemotherapy or immunotherapy agents. On day 1 of induction cycles, Atezolizumab will be administered first, followed by carboplatin, and lastly etoposide. Time intervals between infusions are per institutional standards.

Dose Escalation Schedule								
Dose Level	Induction (Cycles 1-4)				Maintenance (Cycles 5-17)		Cycle Length	
	Dose				Dose			
	Carboplatin	Etoposide	Atezolizumab	Entinostat	Atezolizumab	Entinostat		
Level -1 (ME)	AUC 5 IV D1	100 mg/m  IV D1-3	1200 mg IV D1	None	1200 mg IV D1	5 mg PO D1, 8, 15	21 days	
Level 1*	AUC 5 IV D1	100 mg/m  IV D1-3	1200 mg IV D1	2 mg PO D1, 8, 15	1200 mg IV D1	5 mg PO D1, 8, 15	21 days	
Level 2	AUC 5 IV D1	100 mg/m  IV D1-3	1200 mg IV D1	3 mg PO D1, 8, 15	1200 mg IV D1	5 mg PO D1, 8, 15	21 days	
Level 3	AUC 5 IV D1	100 mg/m  IV D1-3	1200 mg IV D1	5 mg PO D1, 8, 15	1200 mg IV D1	5 mg PO D1, 8, 15	21 days	

\*Starting Dose Level.

IV = intravenous, AUC = Area Under Curve, PO = Orally, ME = Maintenance entinostat.

Regimen Description – Induction (up to 4 cycles) #					
Agent	Premedication; Precautions*	Dose	Route	Schedule	Cycle Length
Entinostat	Take on an empty stomach (at least 1 hour before and 2 hours after a meal)	Assigned dose level	PO	Day 1, 8, 15	21 days (3 weeks)
Atezolizumab		1200 mg	IV infusion over 60 ( $\pm 15$ ) minutes**	Day 1	
Carboplatin	Dexamethasone NK1 antagonist 5-HT3 antagonist.	AUC 5***	IV infusion over 30-60 minutes	Day 1	

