# Patients who are unable to tolerate carboplatin and etoposide, may discontinue induction and receive the maintenance regimen. If this occurs, maintenance may begin prior to Cycle 5 and can continue for a total of 1 year of treatment.

\* Entinostat is taken 1 hour before and 2 hours after a meal.

*\*\*If there is no infusion-related reaction after the initial dose, all subsequent doses of atezolizumab can be infused over 30 ( $\pm 10$ ) minutes.*

*PO = Orally, IV = Intravenous, AUC = Area Under Curve*

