## 6.2 Definition of Dose-Limiting Toxicity

Management and dose modifications associated with the above adverse events are outlined in Section 7.

Dose limiting toxicity (DLT) is defined as the occurrence of any of the following toxicities listed below. The DLT period will be from Cycle 1, Day 1 through the first cycle. To be evaluable for a DLT, at least 66% of the prescribed dose of each drug must be received during cycle 1 (i.e., 2 of 3 doses of entinostat must be received or 66% of prescribed carboplatin, etoposide, or atezolizumab dose must be infused to be considered evaluable if no DLT occurred). If treatment-related adverse events result in <66% of drug doses received, patients will be evaluable for DLTs. Any toxicities attributable to cancer or cancer progression will not be considered DLTs.

DLTs if felt to be possibly, probably, or definitely related to entinostat:

- Less than 66% of entinostat (0 or 1 doses) received during the first cycle due to treatment-related adverse event(s)
- Death in the absence of progressive cancer (Any grade 5 adverse event)
- Any adverse event resulting in discontinuation of carboplatin/etoposide chemotherapy prior to Cycle 2
- Any treatment-related toxicity causing delay of more than 3 weeks from planned cycle 2 day 1
- Any  $\geq$  Grade 3 non-hematologic adverse event (non-laboratory), excluding alopecia, uncontrolled nausea or vomiting. Grade  $\geq 4$  uncontrolled nausea or vomiting should be considered a DLT if it persists  $\geq 72$  hours despite maximal medical management.
- Any  $\geq$  Grade 3 non-hematologic laboratory value if medical intervention is required (not including endocrinopathies requiring hormone replacement) or leads to hospitalization

DLTs regardless of relatedness to entinostat (attribution to any study drug):

- Hematologic events
  - Grade  $\geq 4$  febrile neutropenia
  - Grade 4 neutropenia lasting  $>7$  days
  - Grade 3 thrombocytopenia associated with bleeding requiring transfusion or Grade  $\geq 4$  thrombocytopenia.

Dose escalation will proceed within each cohort of 3 patients according to the following scheme. Dose-limiting toxicity (DLT) is defined above.

Escalation/De-escalation Rule												
Number of patients treated	1	2	3	4	5	6	7	8	9	10	11	12
Escalate if # of DLT $\leq$	0	0	0	0	0	0	1	1	1	1	1	1
Deescalate if # of DLT $\geq$	1	1	1	1	2	2	2	2	3	3	3	3
Eliminate if # of DLT $\geq$	NA	NA	2	3	3	3	4	4	4	5	5	5

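### Dose Level -1 gives no entinostat with carboplatin/etoposide, and the feasibility denominator, the toxicity-evaluability rule and the MTD statement were not adapted to it

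*Combined protocol and SAP*

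**What the plan says.** The dose tables in the Schema and Section 6.1 list no induction entinostat for Level -1, and entinostat with atezolizumab in maintenance. The level carries the tag ME, which the table notes explain: "PO = Orally, ME = Maintenance entinostat". Section 2.4.2.2 discloses the idea: "There will also be a phased-in start of entinostat after the completion of 4 cycles of carboplatin and etoposide, if necessary, due to toxicity". Sections 9.1 and 9.1.3 count Level -1 among the four levels of the BOIN design.

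Three rules meet this level:

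- **Feasibility.** Objective 1.1.3 is "To determine the feasibility of administering entinostat concomitantly with atezolizumab, carboplatin, and etoposide". Section 9.1 makes the number of four-drug cycles (at most 4) a primary endpoint. Section 9.3 says that "the proportion of participants who receive 3 or more cycles of the combination, will be calculated with a 90% confidence interval". No dose level is excluded.
- **Toxicity evaluability.** Section 12.1.1 makes all patients evaluable for toxicity from their first entinostat treatment. Section 6.2 says: "The DLT period will be from Cycle 1, Day 1 through the first cycle". Section 10.3.1 collects every adverse event after baseline, Section 10.4 requires all of them in routine reporting, and the Section 11 calendar schedules adverse event evaluation from Cycle 1 Day 1.
- **MTD.** Objective 1.1.1 is "To determine the maximum tolerated dose (MTD) of entinostat in combination with carboplatin, etoposide, and atezolizumab". Section 9.1.1 selects the level whose isotonic estimate is closest to 20%, with no exception for Level -1. It declares no MTD only when the lowest level is eliminated.

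**The concern.** Each rule reads naturally at Levels 1-3, where entinostat starts on Cycle 1 Day 1. At Level -1 each gives a result that does not answer its objective.

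A Level -1 patient who tolerates everything still scores zero four-drug cycles. Pooling such patients mixes real failures with patients who could not succeed. Read literally, Section 12.1.1 drops Level -1 induction events from the primary Grade 3/4 rate, so that rate would cover different exposure windows at different levels. A Level -1 selection could be written up as the MTD of entinostat in the four-drug combination, although no dose of entinostat given with chemotherapy was selected.

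**Working it through.** **1. Reproducing the plan's table.** Inputs from Sections 9.1, 9.1.1, 9.1.2 and 9.1.3: target 0.20, cohorts of 3, start at Level 1, maximum 36, stop at 12 on a level when the decision is to stay, elimination at posterior probability above 0.95 with a uniform prior, and isotonic selection. The BOIN multipliers 0.6 and 1.4 are an assumption, since the documents do not give them. The resulting boundaries (0.157 and 0.238) match the plan's decision table exactly for 1 to 12 patients. With 10,000 trials per scenario, Level -1 was selected in 2.79/7.16/29.29/50.75% (plan: 2.89/7.41/29.55/51.73%). It held 5.4/10.9/25.8/40.4% of patients (plan: 5.6/10.6/25.7/41.3%). Average size was 23.7/23.8/22.4/19.6 (plan: 23.7/23.7/22.3/19.4). The plan's figures are sound and are used below.

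**2. Four-drug cycles at Level -1.** Induction has no entinostat and maintenance has no carboplatin or etoposide, so the count is zero by schedule. Early maintenance does not change this. Section 6.1 says that after early discontinuation of induction "maintenance may begin prior to Cycle 5 and can continue for a total of 1 year of treatment", but that regimen still lacks the two chemotherapy drugs.

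**3. Expected dilution.** Factor = 1 - share of patients at Level -1. It applies to the proportion and to the mean number of four-drug cycles. No success rate is assumed.

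| | Sc. 1 | Sc. 2 | Sc. 3 | Sc. 4 |
|---|---|---|---|---|
| Share at Level -1 (9.1.3) | 0.056 | 0.106 | 0.257 | 0.413 |
| Average N (9.1.3) | 23.7 | 23.7 | 22.3 | 19.4 |
| Patients at Level -1 (share x N) | 1.3 | 2.5 | 5.7 | 8.0 |
| Patients at Levels 1-3 | 22.4 | 21.2 | 16.6 | 11.4 |
| Dilution factor | 0.944 | 0.894 | 0.743 | 0.587 |

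In the re-simulation at least one cohort entered Level -1 in about 23/36/60/79% of trials. The remaining trials have no dilution.

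An invented single trial shows the effect. With 10 of 12 successes at Levels 1-3, feasibility is 83% (exact 90% CI 56-97%). Adding 12 Level -1 patients makes it 10 of 24, or 42% (25-60%).

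**4. Toxicity window.** At Levels 1-3, entinostat is given on Cycle 1 Day 1; Section 6.1 says that on day 1 "entinostat will be administered prior to other chemotherapy or immunotherapy agents". At Level -1 the first dose normally falls in Cycle 5, after 4 x 21 = 84 days. It comes sooner if maintenance starts early, and never if the patient stops before maintenance.

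**5. No concomitant MTD.** Level -1 selected + stopped early (9.1.3):

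- Scenario 1: 2.89 + 0.1 = 2.99%
- Scenario 2: 7.41 + 0.4 = 7.81%
- Scenario 3: 29.55 + 3.5 = 33.05%
- Scenario 4: 51.73 + 15.1 = 66.83%

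In Scenarios 1-3 a concomitant level has a true DLT rate of exactly 0.20 (Level 3, 2 and 1), so this outcome is a miss. In Scenario 4 the concomitant levels have true rates of 0.28, 0.36 and 0.44, all above target, so it is the right conclusion about concomitant dosing.

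**6. Precision if feasibility uses Levels 1-3.** Worst-case 90% half-width = 1.645 x sqrt(0.25/n). All participants: 16.9/16.9/17.4/18.7 points. Levels 1-3: 17.4/17.9/20.2/24.4 points.

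**The case against.** The best defence is that Level -1 is deliberate, labelled and disclosed. Objective 1.1.3 and Section 9.3 speak of giving entinostat concomitantly, which points to patients assigned that regimen. The feasibility proportion has no success threshold and drives no stopping rule. The Section 12.1.1 sentence sits under antitumor effect, while Section 9.3 summarises adverse events without restricting them to time after entinostat. All of this is fair, and it limits the consequences. But a Levels 1-3 denominator is only an inference. Section 9.3 refers to participants without qualification, and the two readings give different answers. The Section 12.1.1 sentence still conflicts with the safety sections.

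Four stronger readings are tempting but not supported:

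- A reader might take the dilution factors as ceilings on feasibility. They are averages over simulated trials. A trial that never opens Level -1 can reach 100%.
- A reader might infer that Level -1 induction events go uncollected or that DLTs cannot be scored there. Sections 6.2, 10.3.1, 10.4 and 11 show otherwise.
- A reader might equate a Level -1 selection with intolerable Levels 1-3. With 3/12 DLTs at Level 1 (25%) and 2/12 at Level -1 (16.7%), Level -1 is closer to 20% and is selected. Level 1 is not eliminated, because that needs 5 of 12.
- A reader might conclude that the operating characteristics in Section 9.2 are undermined. Relabelling leaves target-dose selection in Scenarios 1-3 at 48.64/38.13/44.92%. In Scenario 4 the right conclusion about concomitant dosing is reached in 66.83% of trials, more than the 51.73% shown for Level -1.

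**Conclusion.** The point holds as a mismatch between three reporting rules and one dose level, and should be fixed before analysis. The dose-finding design itself is sound.

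The feasibility effect is small in Scenario 1 (about 1.3 patients, factor 0.944) and large in Scenarios 3 and 4 (0.743 and 0.587). It rests on the literal reading of Section 9.3 and the average allocation in Section 9.1.3, and disappears if the denominator is Levels 1-3. The toxicity item is a contradiction to reconcile; its effect on the Grade 3/4 rate arises only if Section 12.1.1 is applied literally. The MTD item concerns how a selection is reported, and its frequency depends on the true toxicity, from 2.89% of trials in Scenario 1 to 51.73% in Scenario 4.

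**What to change.** - **1.1.3 and 9.3:** state that the feasibility proportion and the number of four-drug cycles are calculated in patients assigned concomitant entinostat (Levels 1-3), and show both by dose level.
- **12.1.1:** make patients evaluable for toxicity from the first dose of any study drug, so that the Grade 3/4 rate uses the same window at every level.
- **9.1.1:** state that a Level -1 selection is reported as the maintenance-only entinostat regimen, with no MTD of entinostat concomitant with induction chemotherapy selected. Do not describe Levels 1-3 as intolerable unless they were eliminated.
- **9.2 (optional):** if the 3.0/7.8/33.1/66.8% for no concomitant MTD is added, say that this outcome is incorrect in Scenarios 1-3 and the correct conclusion in Scenario 4.

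The cost is a few sentences and a wider feasibility interval, at worst about 24 instead of 19 points half-width in Scenario 4. No new simulation is needed, and allocation, dosing and sample size are unchanged.

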## 9. STATISTICAL CONSIDERATIONS

### 9.1 Study Design/Endpoints

This is a phase 1 trial to evaluate the safety and efficacy of various doses of entinostat combined with atezolizumab, carboplatin, and etoposide therapy for patients with treatment naïve ES-SCLC. Four dose levels of entinostat are detailed in Figure 1. The Bayesian optimal interval (BOIN) design will be used to find the maximum tolerated dose (MTD) based on safety (Liu and Yuan, 2015; Yuan et al., 2016). The target toxicity rate for the MTD is 20%. Due to overlapping hematologic toxicities between chemotherapy and entinostat, it may be difficult to separate attributions specifically to entinostat, particularly for thrombocytopenia events. Our DLT definitions will count these more extreme hematologic events at DLTs, although it is recognized that these occur in the setting of carboplatin and etoposide chemotherapy alone. Therefore, it is anticipated that a 20% DLT rate is a conservative estimate of the true DLTs directly related to entinostat. Furthermore, small cell lung cancer is an aggressive malignancy with poor overall survival. Additional toxicity is justified if there is potential for efficacy gains. Dose-limiting toxicities (DLT) will be determined by adverse events occurring during the first cycle of treatment. DLTs are defined in Section 6.2.

The primary endpoints of the study are:

- MTD of entinostat
- Grade 3/4 adverse event rate as defined by CTCAE v5.0
- Number of cycles received of the combination of entinostat, atezolizumab, carboplatin, and etoposide (maximum = 4)

The secondary endpoint of the study is:

- 9-month PFS rate, defined as the proportion of patients alive and without disease progression after 9 months from study enrollment

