#### 9.1.1 Treatment allocation

Participants will be enrolled and treated in cohorts of size 3. Only DLTs that occur within the first cycle will be used for dose finding. As shown in Figure 2, the BOIN design uses the following rule, optimized to minimize the probability of incorrect dose assignment, to guide dose escalation and de-escalation.

The steps to implement the BOIN design are as follows: 1) Participants in the first cohort are treated at dose level 1; 2) To assign a dose to the next cohort of participants, conduct dose escalation and de-escalation according to the rule displayed in the table below; 3) Repeat step 2 until the maximum sample size of 36 is reached, or stop the trial if the number of participants treated at the current dose reaches 12 and the decision according to the table below is to stay at the current dose.

After the trial is completed, the MTD is determined based on isotonic regression as specified in Liu and Yuan (2015). This computation is implemented by the shiny app “BOIN” available at <http://www.trialdesign.org>. Specifically, the MTD is the dose for which the isotonic estimate of

[figure not shown]
the toxicity rate is closest to the target toxicity rate. If there are ties, the higher dose level will be selected when the isotonic estimate is lower than the target toxicity rate and the lower dose level will be selected when the isotonic estimate is greater than or equal to the target toxicity rate.

At the conclusion of the trial, all available safety data will be reviewed. If a significant number of clinically significant adverse events outside the definition of a DLT occurred at the MTD, the recommended phase 2 dose may be a lower dose level than the MTD. Examples of clinically significant events that would be considered are events similar to DLTs that occurred in later cycles outside the DLT window, treatment discontinuation due to an adverse event attributed to entinostat, or patient withdrawal from the study due to intolerable adverse events.

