## 9.2 Sample Size/Accrual Rate

The maximum sample size is 36 participants and the trial will stop accruing participants once 12 participants have been treated on a single dose level. The maximum target sample size is based on obtaining sufficient information to assess the study aim of establishing the MTD. Operating characteristics provided in the table in section 9.1.3 indicate that the sample size results in a high rate of simulated trials identifying the target dose level as the MTD across multiple dose-toxicity scenarios, highlighting the ability of study design to achieve the primary aim of determining the MTD.

We anticipate accruing 2 patients per month and therefore expect to complete accrual within 18 months.

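### As worded, the feasibility rate is one proportion over all dose levels, including one with no entinostat in induction, so it need not equal the rate at the recommended dose

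*Combined protocol and SAP*

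**What the plan says.** Objective 1.1.3 makes feasibility a primary objective, "as determined by the proportion of patients who receive 3 or more cycles of the combination". The matching primary endpoint in Section 9.1 is "Number of cycles received of the combination of entinostat, atezolizumab, carboplatin, and etoposide (maximum = 4"). Section 9.3 then gives the whole analysis: the "proportion of participants who receive 3 or more cycles of the combination, will be calculated with a 90% confidence interval". None of these places names a dose level, an analysis set or a table by dose.

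The dose table in Section 6.1 (repeated in the Schema) sets induction entinostat at 2, 3 and 5 mg for Levels 1, 2 and 3. At Level -1 the induction entinostat cell is empty of drug: the row reads "1200 mg IV D1 None 1200 mg IV D1" for atezolizumab, entinostat, then maintenance atezolizumab. Carboplatin and etoposide are given only in induction, at every level.

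Section 9.1.1 chooses the MTD from the DLT data and allows a lower recommended phase 2 dose after all safety data have been reviewed. The feasibility rate is not mentioned in that decision.

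**The concern.** The trial ends by naming one dose. A reader will want to know how often three or more cycles can be delivered at that dose. A single proportion over all participants answers a different question: it averages over dose levels with weights set by the escalation path. Section 2.4.2.2 and Section 9.1 both expect overlapping hematologic toxicity between entinostat and chemotherapy, so deliverability may well change with dose.

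The denominator is a second problem. A Level -1 patient receives three drugs in Cycles 1 to 4 and two drugs afterwards, so no cycle contains the four-drug combination. As worded, such a patient cannot succeed. Two analysts could count these patients as failures or leave them out, and report quite different primary results from the same data.

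**Working it through.** **Step 1. Reproduce the plan's table (Section 9.1.3).** Inputs: target DLT rate 20% (Section 9.1); "Participants will be enrolled and treated in cohorts of size 3" (Section 9.1.1); "The maximum sample size is 36 participants" (Section 9.2); start at Level 1; stop when the number at the current dose "reaches 12 and the decision according to the table below is to stay at the current dose" (Section 9.1.1); elimination at posterior probability 0.95 with a uniform prior (Section 9.1.2).

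BOIN boundaries with φ = 0.20 and the usual multipliers 0.6 and 1.4 (φ1 = 0.12, φ2 = 0.28):

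- escalate: ln[(1-φ1)/(1-φ)] / ln[φ(1-φ1)/(φ1(1-φ))] = ln(0.88/0.80) / ln(0.176/0.096) = 0.157
- de-escalate: ln[(1-φ)/(1-φ2)] / ln[φ2(1-φ)/(φ(1-φ2))] = ln(0.80/0.72) / ln(0.224/0.144) = 0.238

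These boundaries and the elimination rule give all three rows of the decision table exactly. With 10,000 simulated trials per scenario:

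| | Sc. 1 | Sc. 2 | Sc. 3 | Sc. 4 |
|---|---|---|---|---|
| Average N, stated | 23.7 | 23.7 | 22.3 | 19.4 |
| Average N, reproduced | 23.7 | 23.7 | 22.3 | 19.6 |
| Target dose selected, stated % | 48.64 | 38.13 | 44.92 | 51.73 |
| Target dose selected, reproduced % | 48.8 | 38.1 | 45.6 | 51.8 |

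The table reproduces, so its allocation percentages can be used as weights. (Section 9.2 words the 12-patient stop without the stay condition. That reading gives average N of only 20.5, 19.6, 18.3 and 16.7, so the table follows 9.1.1.)

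**Step 2. Who is in the pooled denominator.** Patients = stated percentage × stated average N.

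| | Sc. 1 | Sc. 2 | Sc. 3 | Sc. 4 |
|---|---|---|---|---|
| True target dose | Level 3 | Level 2 | Level 1 | Level -1 |
| % at -1 / 1 / 2 / 3 | 5.6 / 27.5 / 34.1 / 32.8 | 10.6 / 37.7 / 33.7 / 18 | 25.7 / 43.7 / 23 / 7.6 | 41.3 / 42 / 13.7 / 2.9 |
| Patients at target dose | 7.8 | 8.0 | 9.7 | 8.0 |
| Patients at Level -1 | 1.3 | 2.5 | 5.7 | 8.0 |

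**Step 3. Ceiling if Level -1 counts as failure.** Even if every other patient succeeds, the expected pooled rate is at most the share treated at Levels 1 to 3:

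- Sc. 1: 27.5 + 34.1 + 32.8 = 94.4%
- Sc. 2: 37.7 + 33.7 + 18 = 89.4%
- Sc. 3: 43.7 + 23 + 7.6 = 74.3%
- Sc. 4: 42 + 13.7 + 2.9 = 58.6%

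This uses only the plan's own percentages.

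**Step 4. Pooled rate against the target-dose rate.** Feasibility by dose is not in the documents. Assume 85/75/55% at Levels 1/2/3. With Level -1 excluded, pooled = Σ(weight × rate) / Σ(weight):

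- Sc. 1: (0.275×85 + 0.341×75 + 0.328×55) / 0.944 = 66.99 / 0.944 = 71.0%, against 55% at Level 3: +16.0
- Sc. 2: (0.377×85 + 0.337×75 + 0.18×55) / 0.894 = 67.22 / 0.894 = 75.2%, against 75% at Level 2: +0.2
- Sc. 3: (0.437×85 + 0.23×75 + 0.076×55) / 0.743 = 58.58 / 0.743 = 78.8%, against 85% at Level 1: -6.2
- Sc. 4: the target is Level -1, where the rate is not defined, so there is no comparison.

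A flatter assumption, 80/75/70%, gives 74.7%, 76.1% and 77.4%, that is +4.7, +1.1 and -2.6 points.

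With Level -1 counted as failure and 85/75/55%, the pooled rates are the numerators above: 67.0%, 67.2% and 58.6%, that is +12, -8 and -26 points. In Scenario 3 the handling of Level -1 alone moves the result by 78.8 - 58.6 = 20 points.

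**Step 5. Precision after the fix.** In the reproduced simulations the selected dose holds a median of 12 patients. Exact (Clopper-Pearson) 90% limits are the 0.05 quantile of Beta(x, n-x+1) and the 0.95 quantile of Beta(x+1, n-x):

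- 9/12: 47.3% to 92.8%, 45.5 points wide
- 18/24: 56.5% to 88.5%, 32.0 points wide

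**The case against.** **Pooling is nowhere stated.** This stands. It is the literal reading of an unqualified denominator, not a declared choice, and the point is worded accordingly.

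**A reader might infer that most of the estimate comes from doses other than the recommended one.** The table does put 56 to 67% of patients away from the true target dose. The recommended dose comes from the selected dose, however, and in the reproduced simulations that level holds on average about 58 to 64% of participants. The pooled rate is diluted, not unrelated.

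**A reader might infer that pooling always flatters the result.** It does not. The gap is large and upward in Scenario 1, near zero in Scenario 2 and downward in Scenario 3, and its size rests on assumed rates.

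**A reader might infer that the wrong dose could be recommended.** The documents do not support this. There is no feasibility threshold, and Section 9.1.1 selects on DLTs and then on safety at the MTD, including discontinuations and withdrawals.

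**A reader might infer that adverse events are pooled too.** Section 9.3 says only that they are summarized by frequency and magnitude. Section 9.1.1 reviews safety at the MTD, and Section 6.2 lets the team act on events in a single cohort. The case for a table by dose is therefore weaker for adverse events than for feasibility.

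**Objective 1.1.3 names no dose, and Section 7.2.1 allows reductions within a level.** Both are true. A rate by assigned level is not a rate for the dose actually delivered. It is still closer to the recommended dose than a mixture of levels.

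**Conclusion.** The point holds in limited form. Followed literally, the plan reports for a primary objective a rate that mixes dose levels and leaves open how to count patients who cannot meet the criterion. Under the assumed 85/75/55% pattern with Level -1 excluded, the gap from the target-dose rate is about +16, 0 and -6 points in Scenarios 1 to 3; a flatter pattern gives about +5, +1 and -3. The ceilings of about 94%, 89%, 74% and 59% need no assumed rates, only the plan's allocation table and the choice to count Level -1 as failure. They are expectations over simulated trials, so one trial's ceiling depends on how many patients it treats at Level -1. The consequence is an ambiguous report of a primary objective. MTD selection is not affected.

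**What to change.** In Section 9.3:

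1. Report the feasibility proportion with an exact 90% interval by assigned dose level and at the selected MTD or recommended phase 2 dose.
2. Define the denominator as treated participants assigned entinostat in induction. Section 4.4 already replaces patients who are registered but never treated.
3. Report Level -1 separately, as neither success nor failure, and say that the four-drug rate is not defined there should that level be selected.
4. Keep any pooled figure as supportive, with the same denominator.
5. Tabulate the Grade 3/4 adverse event rate, the endpoint named in Section 9.1, by dose level in the same table.

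The cost is a few sentences and one table, with no change to sample size, dosing or conduct. The drawback is a wider interval: 47 to 93% for 9/12 at one dose, against 57 to 89% for 18/24 pooled. That width is what about 12 patients at one dose can support.
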